8.4 Final Study Visit

Study Day 365

Allowable window for clinic visit is 365 ±14 days from Study Day 0 visit date.

- 1. Verbally reconfirm consent.
- 2. Update medical history including use of medications.
- 3. Screening for potential new TB exposure and TB symptoms.
- 4. Record feeding practice.
- 5. Vital signs (heart rate, respiratory rate, axillary temperature, weight and recumbent length).
- 6. Focused physical examination.
- 7. Record any serious adverse events (including concomitant medications) and unsolicited adverse events.
- 8. Examine site of injection (includes measurement of redness, swelling, and ulceration) and take a pus swab if discharge present.
- 9. Blood collection for:
 - Immunogenicity WB-ICS
 - QuantiFERON®-TB Gold Plus

Post Cohort Unblinding of Participants Post Study Day 365

Participant, and subsequent clinical team unblinding will occur when all infants in a given cohort have attained their Study Day 365 visit.

- MTBVAC recipients who have tested QFT positive will be given a card stating that they
 have received an investigational vaccine that may interfere with interpretation of future
 IGRA and TST tests.
- BCG rescue dose will be offered to all MTBVAC recipients in this cohort, given that the
 individual recipients have a negative screen for active TB disease and new household
 contacts, and do not have a new positive QFT result at D365. Any MTBVAC recipient
 receiving IPT will be offered the BCG rescue dose after completion of IPT.
- 3. The site will contact the participant's caregiver telephonically (or perform a home visit if no telephone available) 14 days post vaccination with the BCG rescue dose to enquire about the infant's wellbeing and BCG injection site reaction, and respond appropriately to any adverse reaction.

Note: The immunology team will remain blinded until immunology database lock.

8.5 Early Termination Visit

Visit to be conducted if participant discontinues from study prior to Study Day 365.

- 1. Update medical history including use of medications.
- 2. Screening for potential new TB exposure and TB symptoms.
- 3. Record feeding practice.

- 4. Vital signs (heart rate, respiratory rate, axillary temperature, weight and recumbent length).
- 5. Focused physical examination.
- 6. Record any adverse events, including unsolicited adverse events, and serious adverse events (including concomitant medications).
- 7. Examine site of injection (includes measurement of redness, swelling, and ulceration) and take a pus swab if discharge present.
- 8. Blood collection for:
 - QuantiFERON-PLUS TB
 - Confirm contact details for possible BCG rescue dose once all infants in cohort have completed D365 visit.

8.6 Unscheduled Visit

For emergencies and other unscheduled visits to a medical facility other than the study clinic, medical records will, to the extent possible, be obtained by the investigator.

Should visits to the clinical trial site occur outside of the scheduled study visits, these will be documented in the source notes as an unscheduled visit and captured in the Electronic Data Capture system as an unscheduled visit. Data will be reviewed as per all scheduled visits.

9 STUDY PROCEDURES/EVALUATIONS

9.1 Clinical Evaluations

Participants will have vital signs taken prior to study vaccination. Participants will remain in the clinic under close observation for at least 60 minutes after receiving investigational product. Vital signs will be repeated at 60±10 minutes post-vaccination before participants leave the clinic. Allergic reactions to vaccination are possible; therefore, appropriate paediatric drugs and medical equipment to treat acute paediatric anaphylactic reactions must be immediately available, and a medically qualified study team member trained to recognize and treat anaphylaxis must be present in the clinic during the entire vaccination procedure and post-vaccination monitoring period.

Clinical assessments to be performed at each visit are summarized in Appendix A and listed by visit in Section 8.

Participants' caregivers will receive, and be instructed in, the operation of a daily adverse event diary, ruler (for measurement of redness, swelling, and ulceration), and a digital thermometer to measure axillary temperature, to be used during the 7 days post-vaccination diary period after investigational product administration. The daily adverse event diary is a tool to help aid the principal investigator or designee to engage in a conversation with the participant's caregiver about any AEs that may have occurred between visits. During scheduled visits through the specified diary period and after investigational product administration, the daily diary will be collected and reviewed by the principal investigator or designee at which time any clinical details required for complete understanding of the information recorded will be obtained. If possible, diaries not brought to the scheduled visit should be obtained before adverse event assessment can be performed and events discussed with the principal investigator or designee. If a diary is lost, the principal investigator or designee will discuss the occurrence of any solicited adverse events with the participant's caregiver and document the discussion. Information on the diary card will not be directly recorded onto eCRFs. The diary card will be considered source documentation and adverse event information obtained from the diary card will be recorded and completely assessed on the adverse event eCRF. Axillary temperatures below 38°C will not be considered fevers.

Any change to an observation or event recorded by the participant's caregiver on the diary card (e.g., the severity level of an event is changed after interviewing the participant's caregiver), based on the investigator's evaluation of the event, must be explained by notation in source documentation by the principal investigator or designee.

9.1.1 Screening for TB and referral for Isoniazid Preventive Therapy

All infants will undergo screening for potential new TB exposure and TB symptoms at each visit and caregivers will be encouraged to report such symptoms or any new household TB contact if they occur in between visits. If TB symptoms or potential new TB exposure are

detected these infants will be investigated for active TB disease and may be referred to the public health clinic for initiation of TB treatment if indicated or IPT if active TB is ruled out.

Early (D56) post-vaccination QFT conversion in infants with low risk of natural *M. tuberculosis* exposure is assumed to be vaccine-induced and will not be treated with isoniazid preventive therapy (IPT). Infants who demonstrate early QFT conversion at D56 will undergo enhanced screening for potential new TB exposure and TB symptoms during all scheduled study visits, and in addition, during interval telephonic contacts at D120 and D270. QFT samples will be collected at D182 and D365 from infants who tested QFT positive at D56, and stored for later analysis, but since a positive QFT result would not be interpretable, these data will not be used for clinical decision-making. All infants who received MTBVAC and tested QFT positive will receive a card at the end of study indicating that they have received an experimental vaccine that may interfere with interpretation of future IGRA and TST tests for TB infection..

QFT assays will be repeated at D182 and D365 in infants who tested QFT negative at D56. These results will be made available for clinical decision-making. Infants with new QFT conversion events at D182 or D365, and any infant with a reported new household TB contact regardless of QFT status, will be referred to the public health services for IPT since these infants would potentially benefit from TB prophylaxis against *M. tuberculosis* infection as per SA national guidelines, provided that signs and symptoms of active TB disease are absent.

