 To differentiate vaccine-induced immune responses from natural Mtb infection.

[figure not shown]
Design:

Double-blind, randomised, active BCG control, MTBVAC dose-finding trial with 3 cohorts of healthy, BCG naïve, HIV unexposed, South African newborns (24 BCG; 75 MTBVAC)

Estimated Time to Complete Enrollment:

The estimated time to complete enrollment is approximately 9 months.

Schematic of Study Design:

¹ Cohort 1: n=25 MTBVAC (2.5 x 104 CFU) and n=8 BCG

² Cohort 2: n=25 MTBVAC (2.5 x 10⁵ CFU) and n=8 BCG

³ Cohort 3: n=25 MTBVAC (2.5 x 106 CFU OR 2.5 x 105 CFU (n=13) plus 2.5 x 104 CFU (n=12)) and n=8 BCG

⁴ At each DSMB, all available safety data from previous cohorts enrolled will be reviewed. If any of the safety criteria is not met for the 2.5 x 10° CFU dose for Cohort 3, Cohorts 1 and 2 will be expanded so that 33 additional neonates will be randomly allocated to receive the 2.5 x 10° CFU dose (n=13), the 2.5 x 10° CFU dose (n=12) or BCG (n=8) by default.

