skin test (TST) conversion. Three of 8 (37,5%), six of 8 (75%) and 7 of 9 (77,8%) infants who received MTBVAC at 2.5 x 10³, 2.5 x 10⁴ and 2.5 x 10⁵ dose respectively, demonstrated a positive QuantiFERON (QFT) test 180 days after MTBVAC administration, in the absence of known exposure to TB, compared to none of seven BCG recipients. At one year of age none of 8 (0%), two of 8 (25%) and 4 of 9 (44%) infants who received MTBVAC at 2.5 x 10³, 2.5 x 10⁴ and 2.5 x 10⁵ dose respectively, demonstrated a positive QFT result. This new data offers a strong indication of the immunogenicity of MTBVAC in newborns, which requires confirmation in a larger study. Further, since QFT conversion is used as a tool to diagnose *M. tuberculosis* infection in adults and older children, and as an endpoint in exploratory prevention of *M. tuberculosis* infection (POI) vaccine trials, it is critical that the mechanism of MTBVAC-induced QFT conversion and reversion is fully explored. If MTBVAC is shown to be efficacious against TB disease, these data will be important for development of alternative interferongamma release assays (IGRA) for *M. tuberculosis* infection that are not cross-reactive with MTBVAC.

Biofabri, industrial manufacturer and exclusive licensee of MTBVAC, together with intellectual property owner Unizar, has set two independent clinical development pathways for MTBVAC. One pathway focuses on development of MTBVAC for prevention of TB disease in previously BCG vaccinated adults. This clinical trial is based on the clinical development pathway of MTBVAC as a preventive pediatric vaccine that could potentially replace newborn BCG vaccination. A Phase 2a dose-defining study is a pre-requisite for selecting optimal dose for future efficacy trials of MTBVAC in newborns in TB endemic countries.

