It is not yet known whether MTBVAC offers equivalent, better, or worse protection against TB compared to BCG. Therefore, measures to minimize risk of TB will be put in place throughout the study and, after completion of all Study D365 visits in each cohort and unblinding of the clinical team, 'catch up' BCG vaccination will be given to all MTBVAC vaccinated infants once the last participant of each cohort has performed the D365 visit, provided that the individual recipients have a negative screen for active TB disease and new household contacts, and do not have a new positive QFT result at D365. Risk of incident TB disease will be minimized by exclusion of infants with known TB exposure, including prior maternal or family history. Newborns born to HIV infected mothers, with increased risk of TB, will not be enrolled. All infants will be screened actively for TB symptoms at each study visit to diagnose TB disease early and pre-empt severe morbidity. Infants diagnosed with TB disease will remain in safety follow-up, but will be referred immediately for TB treatment, provided free of charge by health services. In the previous South African study we saw no confirmed TB cases in either adults or infants who received MTBVAC. One adult MTBVAC recipient with recent HIV seroconversion was diagnosed with aseptic meningitis and received 6 months treatment for unconfirmed TB meningitis. Two infant MTBVAC recipients (one QFT+; one QFT-) received TB treatment in the public health system for unconfirmed TB; a rate (2/28; 7%) that is similar to the rate of unconfirmed TB in a previous infant trial in this community (13% over 2 years)[29]

The QFT assay is widely used in older children and adults as a tool to aid in the diagnosis of *M. tuberculosis* infection. Given the preliminary evidence of MTBVAC vaccine induced QFT conversion in the current Phase 1b infant study, it is postulated that infants who receive MTBVAC will demonstrate QFT conversion events two months after vaccination (D56), followed by a high rate of reversion, leading to declining rates of QFT positivity at D182 and D365. The same response kinetic was observed for BCG-specific T cell responses in a prior longitudinal study in newborns (15). The observed effect of MTBVAC on QFT conversion is analogous to the known effect of BCG on false positive TST conversion; MTBVAC might be expected to have a similar effect on TST conversion.

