Based on observed rates of QFT positivity 1 year after MTBVAC vaccination in infants, half or more of infants who receive MTBVAC may remain QFT positive at end of study and longer. However, it will not be possible to differentiate MTBVAC-induced QFT conversion from QFT conversion as a consequence of natural *M. tuberculosis* infection. Therefore, risk of natural *M. tuberculosis* infection will be minimized by exclusion of infants with known TB exposure, including prior maternal or family history. Infants who demonstrate QFT conversion soon after

MTBVAC administration are more likely to have converted due to vaccine effect than infants who demonstrate QFT conversion later during follow-up, who are more likely to have converted due to natural *M. tuberculosis* infection. Early (D56) post-vaccination QFT conversion in infants with low risk of natural *M. tuberculosis* exposure is assumed to be vaccine-induced and will not be treated with isoniazid preventive therapy (IPT). Infants who demonstrate early QFT conversion at D56 will undergo enhanced screening for potential new TB exposure and TB symptoms during all scheduled study visits, and in addition, during interval telephonic contacts at D120 and D270. QFT samples will be collected at D182 and D365 from infants who tested QFT positive at D56, and stored for later analysis, but since a positive QFT result would not be interpretable, these data will not be used for clinical decision-making. All infants who received MTBVAC and tested QFT positive will receive a card at the end of study indicating that they have received an experimental vaccine that may interfere with interpretation of future IGRA and TST tests for TB infection.

QFT assays will be repeated at D182 and D365 in infants who tested QFT negative at D56. These results will be made available for clinical decision-making. Infants with new QFT conversion events at D182 or D365, and any infant with a reported new household TB contact regardless of QFT status, will be referred to the public health services for IPT since these infants would potentially benefit from TB prophylaxis against *M. tuberculosis* infection as per SA national guidelines, provided that signs and symptoms of active TB disease are absent.

Known Potential Benefits

All infant participants will benefit from enhanced TB screening and facilitated referral and improved access to healthcare providers.

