6.2 Participant Exclusion Criteria

Participants must have none of the following at the time of randomization:

- 1. Participant must not have received BCG vaccination prior to enrolment.
- 2. Significant antenatal or intrapartum complications that may affect the health of the neonate.
- 3. Skin condition, bruising or birth mark at the intended injection site.
- 4. Maternal HIV test (rapid test, ELISA or PCR) not performed within 30 days of delivery, HIV test results not available, or HIV test result known positive.
- 5. History of close contact with a TB patient, antenatal or postnatal, whether maternal, other family member or another household member who has not yet completed TB treatment.
- Clinically suspected neonatal sepsis.
- 7. Any severe congenital malformation.
- 8. History or evidence of any systemic disease on examination, or any illness that in the opinion of the investigator may interfere with the evaluation of the safety and immunogenicity of the vaccine. Neonatal jaundice not considered clinically significant is not an exclusion.

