- Record any adverse events, including unsolicited adverse events, solicited and unsolicited injection site reactions, and serious adverse events (including concomitant medications).
- 8. Examine site of injection (includes measurement of redness, swelling, and ulceration) and take a pus swab if discharge present.
- 9. Blood collection for:
 - Immunogenicity WB-ICS
 - QuantiFERON®-TB Gold Plus test

Study Day 120 ±7 days and Study Day 270 ±7 days

Home / telephonic visit if infant tested QFT positive at D56 to enquire about TB signs and symptoms and general well-being

Study Day 182

Allowable window for clinic visit is 182 ±14 days from Study Day 0 visit date.

- 1. Verbally reconfirm consent.
- 2. Update medical history including use of medications.
- 3. Screening for potential new TB exposure and TB symptoms.
- 4. Record feeding practice.
- 5. Vital signs (heart rate, respiratory rate, axillary temperature, weight and recumbent length).
- 6. Focused physical examination.
- 7. Record any adverse events, including unsolicited adverse events and serious adverse events (including concomitant medications).
- 8. Examine site of injection (includes measurement of redness, swelling, and ulceration) and take a pus swab if discharge present.
- 9. Blood collection for:
 - Immunogenicity WB-ICS
 - QuantiFERON®-TB Gold Plus

Partial Cohort Unblinding of Data Post Study Day 182

Once the last Cohort 3 Study D182 visit has been completed, an independent biostatistician be unblinded to available study data. At this point Cohort 1 and Cohort 2 participants will have completed all study visits and these participants and clinical team will be unblinded post Study D365 visit. All available safety data for all cohorts up to the last Cohort 3 Study D182 visit completion; and immunogenicity data for all cohorts up to each cohort's Study D182 visit, will be analysed by the independent, unblinded biostatistician and provided to DSMB for review to determine MTBVAC dose selection for the Phase III study. The Sponsor will review blinded data only in order to keep the blind until post Study D365 visit. The DSMB will be provided with the same blinded data along with unblinding vaccine recipient lists. The DSMB review will allow for a blinded recommendation and input into the dose selection for the Phase III study. For all cohorts, unblinding of the clinical team and participants will take place post Study D365 visit.

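### After cohort unblinding, no step revisits a BCG recipient who was QFT-positive at D56, although the vaccine-effect reasoning covers MTBVAC only

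*Combined protocol and SAP*

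**What the plan says.** **The rule.** Sections 3.3.1 and 9.1.1 carry the same rule for all infants. A D56 QFT conversion in infants at low risk of natural *M. tuberculosis* "exposure is assumed to be vaccine-induced and will not be treated with isoniazid preventive therapy (IPT"). QFT samples from these infants at D182 and D365 are taken and stored (also Table 9-1, footnote c), but "since a positive QFT result would not be interpretable, these data will not be used for clinical decision-making".

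**The reasoning.** In section 3.3.1, "it is postulated that infants who receive MTBVAC will demonstrate QFT conversion events two months after vaccination (D56"), and infants who convert soon after "MTBVAC administration are more likely to have converted due to vaccine effect than infants who demonstrate QFT conversion later during follow-up". The only QFT figure for BCG is in section 3.2, where Phase 1b positivity at day 180 after MTBVAC is "compared to none of seven BCG recipients".

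**The safeguards.** Section 6.2 excludes infants with "History of close contact with a TB patient, antenatal or postnatal". All infants are screened for TB symptoms and exposure at each visit. For D56-positive infants, section 8.3 adds at D120 and D270 a home or "telephonic visit if infant tested QFT positive at D56 to enquire about TB signs and symptoms and general well-being". Section 9.1.1 refers two groups for IPT in either arm, provided active TB is absent: infants negative at D56 who convert at D182 or D365, and any infant with a reported new household contact, whatever the QFT result.

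**After unblinding.** Section 8.4 unblinds a cohort when all its infants have reached D365. It then lists three steps: a card for QFT-positive MTBVAC recipients, rescue BCG for MTBVAC recipients, and a call 14 days after rescue BCG. Section 15.1 has the family told which vaccine was given. The Post D365 column of Appendix A marks a TB screen and a physical examination, but no QFT.

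**The concern.** The rule withholds IPT because a D56 conversion is put down to the vaccine. That argument is made for MTBVAC. For an infant known to have received BCG, the documents offer no reason to prefer a vaccine effect, so natural infection has to be considered. Yet the rule is not limited to MTBVAC recipients once the arm is known, and no step reopens the question.

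At stake is the care of a well infant with an unrecognised source case. Screening by symptoms and reported contacts can miss that infant, and it is the infant for whom a positive QFT adds information.

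**Working it through.** The plan states no figure on this point to reproduce. The check sets the sections side by side; the arithmetic only gives scale.

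**1. Does any stated reason reach BCG recipients?** No. The Phase 1b finding (section 3.2), the postulated D56 timing and the early-versus-late argument (section 3.3.1) all name MTBVAC. Section 3.3.1 likens MTBVAC's effect on QFT to BCG's effect on the skin test; it does not say that BCG converts QFT. The BCG result of 0/7 is at day 180, not D56. Its exact two-sided 95% upper limit is 1 − 0.025^(1/7) = 41%, so it neither supports nor refutes the assumption for BCG.

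**2. What happens to a QFT-positive BCG recipient?**

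| First positive | While blinded | After unblinding (8.4) |
|---|---|---|
| D182 or D365 | Referred for IPT if active TB is absent | Already referred |
| D56 | No IPT on the result; extra screening; later QFT data not used clinically | No step |

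**3. How many infants could be affected?** There are 3 × 8 = 24 BCG recipients among 3 × 25 + 3 × 8 = 99 infants (24/99 = 24%). The documents give no D56 positivity rate for BCG, so the rate r, from any cause, is an assumption. The expected number is 24r, and the chance of at least one is 1 − (1 − r)^24.

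| Assumed r | Expected number | Chance of at least one |
|---|---|---|
| 1% | 0.24 | 21% |
| 2% | 0.48 | 38% |
| 5% | 1.2 | 71% |
| 10% | 2.4 | 92% |

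**4. Is the blinded rule reasonable?** Assume that the Phase 1b day-180 rates at the two lower doses of this trial (6/8 and 7/9) also hold at D56. Each cohort of 25 MTBVAC and 8 BCG infants then has 25 × 6/8 = 18.75 or 25 × 7/9 = 19.44 MTBVAC positives, against 8 × 1% = 0.08 to 8 × 10% = 0.8 BCG positives. A D56 positive is an MTBVAC infant with probability between 18.75/(18.75 + 0.8) = 95.9% and 19.44/(19.44 + 0.08) = 99.6%. On these assumptions, yes.

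**5. How old is the D56 result at review?** At the infant's own D365 visit it is 365 − 56 = 309 days old, about 10 months. The minimum within visit windows is (365 − 14) − (56 + 7) = 288 days. Waiting for the rest of the cohort can add to this.

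**6. How much does an old D56 positive mean?** As an illustration, with all values assumed: 0.5% to 3% of BCG infants infected by D56, sensitivity 100%, false positives 1% to 3%. The share of positives truly infected runs from 0.005/(0.005 + 0.995 × 0.03) = 14% to 0.03/(0.03 + 0.97 × 0.01) = 76%. A D56 positive warrants review, but it is weak ground for IPT on its own, so the stored later results should be read first.

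**The case against.** The strongest reply is that the written rule lapses by its own logic. Its premise is an MTBVAC effect, so it has no force for an infant known to have received BCG. Section 10.2.4 has the investigator review results and manage the participant under site policy, and section 10 gives authority to act for safety. A reader might therefore go too far in inferring that the protocol forbids action; it does not. What remains is that this general authority does not withdraw a specific instruction, and the specific steps in section 8.4 pass these infants by.

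Three other stronger readings are tempting and are not supported:

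- **That the blinded handling is wrong.** Acting by arm before D365 would reveal allocation, and on the stated assumptions nearly all D56 positives are MTBVAC infants.
- **That these infants go unmonitored.** The entry exclusion, enhanced screening, D120 and D270 contacts, and IPT referral for any new household contact apply to both arms.
- **That the review delay can be put at a definite longer figure.** The Protocol Summary says "The estimated time to complete enrollment is approximately 9 months", which invites an even split over three cohorts. On that split Cohort 3 finishes D182 at about month 9 + 6 = 15 and Cohort 2 finishes D365 at about month 6 + 12 = 18. Section 8.3 expects Cohorts 1 and 2 to have completed all visits by the last Cohort 3 D182 visit, so the split does not fit the plan.

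It is also fair to object that the Post D365 contact may be meant only for rescue BCG. Appendix A sets no arm restriction and section 6.3.2 speaks of the last participant of each cohort, but section 8.4 describes only MTBVAC steps. The documents do not settle this.

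**Conclusion.** The gap is real and narrow. It opens at cohort unblinding, concerns only BCG recipients who were QFT-positive at D56, and treats them differently from BCG recipients who convert later without giving a BCG-specific reason. That conclusion rests on the text alone.

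Its size rests on assumption. The ceiling is 24 infants, the true number may be zero, and the rates used above have no source in the documents. A reader might infer from 0/7 that a D56-positive BCG infant must be naturally infected; seven infants at day 180 cannot show that, and false positives are possible. No estimate, comparison or dose decision changes. This is a minor participant-safety fix.

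**What to change.** Add one step to Post Cohort Unblinding in section 8.4:

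1. Identify any BCG recipient who was QFT-positive at D56.
2. Make that infant's stored D182 and D365 QFT results available to the clinical team. If they have not been assayed, run them in a coded batch with all D56-positive infants, so that the immunology team stays blinded.
3. Assess the infant for active TB and, if it is excluded, refer for IPT consideration under national guidelines.

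In sections 3.3.1 and 9.1.1, limit the vaccine-effect assumption and the statement that later results cannot be interpreted to MTBVAC recipients once the arm is known. State whether the Post D365 contact includes these BCG recipients. Leave the blinded handling as it is.

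The cost is a short amendment with no new blood draw, because the D182 and D365 samples are already collected. Assays not yet run may have to be brought forward. A D56-positive BCG recipient may need one extra contact if Post D365 was meant only for rescue BCG. The drawbacks are that the D56 result is about 10 months old or more at review and that some of these positives may be false. Reading the later results first limits the second problem; acting sooner would reveal the arm.
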